3.4. Sample Size / Power Calculations

To estimate a proportion of 50% (maximum variability), with a margin of error of +/- 6 percentage points and a confidence level of 95%, a sample size 267 patients will be required.

Assuming 10% of patients with non-available data from the medical records, total sample size must be 300 patients.

The study sample size must allow the estimation of dichotomic variables and to determine the percentage of compliance of each quality care indicator established by the GEMA guidelines. This percentage will allow to establish the degree of compliance of each group of indicators in the site.

The study sample size must allow the estimation of dichotomic variables and to determine the percentage of compliance of each quality care indicator established by the GEMA guidelines. This percentage will allow to establish the degree of compliance of each group of indicators in the site.

Since the primary objective includes a large number of parameters and a descriptive analysis will be done, the sample size (N) has been calculated based on statistical criteria, using the criterion of maximum indeterminacy, when the percentage of one category in a categorical variable is expected to be around 50%. To estimate a proportion of 50%, with a margin of error of +/- 6 percentage points and a confidence level of 95%, a sample size 267 patients will be required. Assuming 10% of patients with non-available data from the medical records, total sample size must be 300 patients.

3.5. Hypotheses

Given that the primary objective aims to obtain an estimation for a population parameter, there is no need for a hypothesis contrast.

4. DATA ANALYSIS CONSIDERATIONS

Data analysis will be performed using SAS Enterprise Guide Version 7.15, and a statistical analysis plan will be designed and agreed before the data analysis initiation.

All the analyzes will be performed by descriptive statistical methods of all the variables separately. All the patients participating in the study who met the eligibility criteria will be included in the study population.

The quantitative data will be described by the following statistical parameters: number of valid patients (N valid), number of missing data (N missing), mean, standard deviation, median, interquartile range, minimum and maximum will also be presented.

The qualitative data will be presented through the length-frequency distributions (absolute and relative). For both cases, the following will be specified: number of observations (N) and number of missing data (N missing).

Primary objective:

To analyze the primary objectives, it will be assessed the percentage of compliance of each asthma quality care indicator established by GEMA guidelines (GEMA 4.4, Guía Española para el Manejo del Asma):

GROUP I. Diagnosis

- Diagnostic confirmation by spirometry and bronchodilator test. To know the compliance of this indicator, it will be calculated the percentage of asthmatic patients diagnosed using spirometry and bronchodilator test will be determined:

Nº patients diagnosed with asthma using spirometry x 100 / nº patients diagnosed with asthma

- Sensitization study in allergic asthma. To know the compliance of this indicator, it will be calculated the percentage of patients with a diagnosed history of suspected allergic asthma included in a sensitization study with different allergens:

Nº of patients with a diagnosed history of suspected allergic asthma included in a sensitization study with different allergens x 100 / nº patients diagnosed with asthma (and diagnosed history of suspected allergic asthma?)

GROUP II. Non-pharmacological treatment

- Smoking cessation. To know the compliance of this indicator, it will be calculated the percentage of asthmatic smokers with documented recommendations for smoking cessation:

Nº of asthmatic smokers with a documented recommendation for smoking cessation x 100 / nº asthmatic smokers

- Educational plan for patients with asthma. To know the compliance of this indicator, it will be calculated the percentage of patients included in an educational plan:

Nº of patients with asthma included in an educational plan x 100 / Nº of patients with asthma

GRUPO III. Pharmacological treatment

- Treatment of choice for persistent asthma. To know the compliance of this indicator, it will be calculated the percentage of patients in treatment for persistent asthma who are receiving inhaled glucocorticoids (ICS):

Nº of patients in treatment for persistent asthma receiving inhaled glucocorticoids (at patient's inclusion date) x 100 / Nº of patients in treatment for persistent asthma

- Treatment for asthma in pregnant women. To determine the compliance of this indicator, it will be calculated the percentage of pregnant women (if applicable) with asthma who maintain their treatment plan based on B2-adrenergic agonists and inhaled corticosteroids among the total pregnant asthmatic women recruited in the study:

Nº of pregnant women with asthma patients who maintain their treatment plan based on B2-adrenergic agonists and inhaled corticosteroids x 100 / Nº of pregnant women receiving asthma maintenance treatment

GRUPO IV. Monitoring

- Periodic monitoring of patients. To determine the compliance of this indicator, it will be calculated the percentage of scheduled monitoring visits per patient and per year during the previous year among asthmatic patients with asthma monitored per year:

Nº of scheduled (not unexpected) monitoring visits per patient and per year x 100 / Nº of patients with asthma monitored per year.

- Periodic monitoring of exacerbations. To determine the compliance of this indicator, it will be calculated the percentage of asthmatic patients with evaluation and documentation of exacerbations:

$$\frac{\text{Nº of patients with asthma with evaluation and documentation of exacerbations during the last year}}{\text{Nº of patients with asthma}} \times 100$$

The interpretation of the result will be subject to the subsequent Statistical Analysis Plan (SAP) which will be determine whether an interpretation of the results obtained will be made or if it will be based on a descriptive definition thereof.

In order to describe the secondary endpoint, the following measures will be described:

- Sociodemographic and clinical characteristics: A descriptive analysis will be performed of the patient's sociodemographic and clinical characteristics collected.
- Treatment patterns: To evaluate this endpoint it will be performed a treatment description of the long-term treatment and the reliever therapy (if applicable).
- To describe the disease control level in the study population. A descriptive analysis will be performed of the disease control level.
- Use of assistance health resources (secondary objective 3): resource use will be evaluated as number of visits performed by the patient the prior year to the inclusion date:
 - Emergency department (ED) linked to asthma.
 - Hospitalizations linked to asthma.
 - Primary care visits (scheduled and unexpected) linked to asthma.
 - Specialist visits (allergists, pulmonologists, etc.) linked to asthma.
- To describe the number of patients with discontinuation of SABA within the last year: It will be described the number of patients with SABA discontinuation during the prior year of the study inclusion date.
-

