2. OBJECTIVES

2.1. Primary objective:

- To describe the clinical management in asthmatic patients in the influential area of Hospital Universitario Virgen de la Victoria according to the assistant quality indicators established by GEMA guidelines (Appendix 1), which are the following:
 - Diagnostic confirmation by spirometry with test bronchodilator. The diagnostic confirmation of the patients with asthma is done with spirometry and bronchodilator test as an objective measure of functional impairment.
 - Sensitization study in allergic asthma. To patients with suspicion of allergic asthma should be performed a study of possible sensitization to different allergens.
 - Smoking cessation. It is recommended smoking cessation to smokers with asthma.
 - Educational plan in patients with asthma. Patients with asthma must follow a basic education program (formed by: knowledge about their illness, about their treatment, action plan and inhalation technique, documented in writing) as part of their treatment.
 - Treatment of choice in persistent asthma. The treatment of choice in persistent asthma includes inhaled glucocorticoid (IGC) used daily. In some justified cases, alternative treatment with leukotriene receptor antagonists can be considered.
 - Asthma treatment in pregnant women. In asthma maintenance treatment in pregnant woman is recommended to keep the commonly used drugs (agonists β_2 -adrenergic and inhaled glucocorticoids).
 - Periodic follow-up of patients. Necessity to make periodic monitoring of patients, even if they have not suffered exacerbations, through scheduled medical visits.

- Periodic record of exacerbations. The specific assessment of exacerbations is evaluated periodically.

2.2. Secondary objectives:

- To describe the sociodemographic and clinical characteristics of the study population.
- To describe the treatment patterns (maintenance treatment, reliever treatment, type of treatment) during the last year.
- To describe the disease control level in the study population.
- To describe the use of resources (emergency visit, Primary care visits, specialist visits) during the last year.
- To describe the number of patients with discontinuation of SABA within the last year and the potential impact on disease control level and use of resources.

For descriptive purposes, an analysis of the objectives will be made based on the level of disease control.

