3.3.1. Endpoints

3.3.1.1. Primary Endpoint

1. The primary endpoint of this study is the asthma management of the study population according to GEMA healthcare quality indicators previously defined. For this assessment, it will be determined the following calculations:
 - I. Percentage of asthmatic patients diagnosed using spirometry and bronchodilator (PBD) test.
 - II. Percentage of patients with a diagnosed history of suspected allergic asthma included in a sensitization study with different allergens.
 - III. Percentage of asthmatic smokers with documented recommendations for smoking cessation.

- IV. Percentage of patients included in an educational plan.
- V. Percentage of patients in treatment for persistent asthma* receiving inhaled glucocorticoids (ICS).
- VI. Percentage of pregnant women (if applicable) with asthma who maintain their treatment plan based on B2-adrenergic agonists and inhaled corticosteroids among the total pregnant asthmatic women recruited in the study.
- VII. Percentage of scheduled monitoring visits per patient and per year during the previous year among asthmatic patients with asthma monitored per year.
- VIII. Percentage of asthmatic patients with evaluation and documentation of exacerbations.

** Persistent asthma can have asthma symptoms on more than 2 days per week and nighttime awakenings once or twice each month.*

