3.3.1.2. Secondary Endpoint(s)

- Demographic characteristics.
 - Age
 - Gender: male, female.
 - Ethnicity: Caucasian / Hispanic / African / Asian / Other / Unknown
 - Weight (kg) and height (cm): BMI autocalculated by the eCRF.
 - Pregnancy status (yes/no)
 - Smoking status (current smoker, ex-smoker*, non-smoker)
- **It will be considered that the patient is ex-smoker since the 6 months of non-smoking.*
- Clinical characteristics:
 - Age at asthma diagnosis
 - Spirometry and bronchodilator test at diagnose
 - Patient's derivation: primary care / specialized healthcare

- Asthma severity degree according to GEMA guidelines: Mild intermittent, Mild persistent, Moderate persistent and Severe persistent.
- Asthma disease control level according to:
 - Clinical criteria (number of SABA canisters retired from the pharmacy in the previous year, number of OCS retired from the pharmacy in the previous year, number of emergency service visits in the previous year, number of unscheduled primary care visits in the previous year).
 - Asthma Control Test (ACT) (most recent value available): No / Yes, specify score: ACT \geq 20 points (controlled) / ACT less than 20 uncontrolled.
- History of allergic asthma (or suspected): No / Yes.
- Sensitization to allergen study (for those patients with a diagnosed history of suspected allergic asthma).
- Registration of asthma education programs performed (last asthma education program performed by the patient): year when it was performed.
- Current asthma therapeutic level according to GEMA stepwise therapy (at patient's inclusion date): Step 1 / Step 2 / Step 3 / Step 4 / Step 5 / Step 6.
- Comorbidities (at patient's inclusion date) according to Charlson Comorbidity Index (autocalculated). A list of diseases will be displayed in order to be selected those the patient suffers at the inclusion date. The Charlson Comorbidity index score will be autocalculated automatically by the eCRF.
- Maintenance/long-term and reliever treatment prescribed for asthma (at inclusion date): type (SABA, LABA, GCI, LTRA, Biologic, immunomodulator, others), initiation date, end date or if its ongoing. Maintenance/long-term and reliever treatment prescribed for asthma in pregnant women (at inclusion date): type (SABA, LABA, GCI, LTRA,

Biologic, immunomodulator, others), initiation date and end date or if its ongoing.

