7.2. External Expert/Health Care Professionals (Consultants & Research PIs)

APPENDIX 1. Quality assistance indicators – GEMA Guidelines

INDICATOR GROUPS	INDICATOR	CALCULATION
I. Diagnosis	1. Diagnostic confirmation by spirometry with bronchodilator test. Diagnostic confirmation of patients with asthma is performed with spirometry and bronchodilator test as an objective measure of functional involvement.	Number of patients with asthma with spirometry performed x100/number of patients diagnosed with asthma.
	2. Sensitization study in allergic asthma. Patients with suspected allergic asthma should be screened for possible sensitizations to different allergens.	Number of patients diagnosed with a history suggestive of allergic asthma with a sensitization study performed to different allergens x100/number of patients diagnosed with asthma.
II. Non-pharmacological treatment	3. Smoking cessation. Smoking cessation is recommended in smoking patients with asthma.	Number of asthma patients with smoking and registered dishabituaction recommendation x100/asthma patients with smoking.
	4. Educational plan for patients with asthma. Patients with asthma should follow a basic education program (consisting of: knowledge about their disease, about its treatment, action plan and inhalation technique, written document) as part of their treatment.	No. of asthma patients with asthma education program x100/no. of asthma patients.
III. Pharmacological treatment	5. Treatment of choice in persistent asthma. The treatment of choice in persistent asthma includes inhaled glucocorticoid (ICG) used daily. In some justified cases, leukotriene receptor antagonists may be considered as an alternative treatment.	Number of patients on control treatment for persistent asthma receiving GCI x 100/number of patients on control treatment for persistent asthma.
	6. Treatment of asthma in pregnant women. In the maintenance treatment of asthma in pregnant women, it is recommended to maintain the drugs usually used (β 2-adrenergic agonists and inhaled glucocorticoids).	No. of women with asthma who maintain their usual treatment (β 2-adrenergic agonists and inhaled glucocorticoids) in pregnancy x100/number of pregnant women with asthma on maintenance treatment.

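### Primary indicator 2 (sensitization study) has no settled denominator, and the all-asthma base in Appendix 1 measures case mix as well as testing; the indicator 1 formula also leaves out the bronchodilator test

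*Combined protocol and SAP*

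**What the plan says.** **Indicator 2.** Section 2.1 sets the primary objective as describing management "according to the assistant quality indicators established by GEMA guidelines (Appendix 1"). The places that define this indicator read as follows.

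- Section 2.1, objective: "To patients with suspicion of allergic asthma should be performed a study of possible sensitization to different allergens".
- Section 3.3.1.1, endpoint II: "Percentage of patients with a diagnosed history of suspected allergic asthma included in a sensitization study with different allergens". No denominator is printed, but the wording implies the suspected-allergic group.
- Section 4, sentence introducing the formula: "it will be calculated the percentage of patients with a diagnosed history of suspected allergic asthma included in a sensitization study with different allergens".
- Section 4, denominator of the formula: "nº patients diagnosed with asthma (and diagnosed history of suspected allergic asthma", then a question mark and a closing bracket.
- Appendix 1, indicator text: "Patients with suspected allergic asthma should be screened for possible sensitizations to different allergens".
- Appendix 1, calculation: patients with a history suggestive of allergic asthma "with a sensitization study performed to different allergens x100/number of patients diagnosed with asthma".

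Section 3.3.1.2 collects "History of allergic asthma (or suspected): No / Yes" and lists the sensitization item only for patients with suspected allergic asthma.

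**Indicator 1.** The objective, endpoint I and the introducing sentence in Section 4 all require spirometry and a bronchodilator test. The formulas in Section 4 and Appendix 1 count spirometry only. Section 3.3.1.2 lists the two tests as one combined item.

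**The concern.** The Section 4 formula for indicator 2 cannot be programmed without a choice that the protocol does not make. The only complete formula is the one in Appendix 1. Its numerator is confined to patients with suspected allergic asthma, but its denominator is everyone with asthma. That includes patients to whom the standard does not apply and for whom the sensitization item is not listed.

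Section 4 says that it assesses the percentage of compliance with each indicator, and the introduction wants the results to show where care can improve. A ratio that falls because fewer patients are allergic cannot serve that purpose by itself. The plan's other subgroup indicators do not have this difficulty: those for smokers, persistent asthma and pregnancy each divide by a subgroup to which the standard applies.

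For indicator 1, a patient with spirometry but no bronchodilator test could be counted as compliant under the written formula, although the endpoint would not count that patient.

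**Working it through.** **The plan's own figure.** Inputs from Section 3.4: proportion 50%, margin 6 points, confidence 95%, 10% unavailable data, total 300.

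- n = 1.96² × 0.5 × 0.5 / 0.06² = 266.8, rounded up to 267. This agrees with the plan.
- 267 / 0.9 = 296.7, so 297; the plan takes 300. Evaluable: 300 × 0.9 = 270, which is at least 267.

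**Indicator 2, effect of the base.** Let s be the share of asthma patients with suspected allergic asthma and c the share of those who had a sensitization study. Neither is in the documents, so both are assumed over a range.

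- Restricted base: the indicator equals c.
- All-asthma base: the indicator equals c × s, with ceiling s at c = 100%.

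| s (assumed) | all-asthma base, c = 80% | ceiling | restricted base |
|---|---|---|---|
| 0.5 | 0.8 × 0.5 = 40% | 50% | 80% |
| 0.7 | 0.8 × 0.7 = 56% | 70% | 80% |
| 0.9 | 0.8 × 0.9 = 72% | 90% | 80% |

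The all-asthma ratio also cannot tell two very different situations apart: s = 50% with c = 90% gives 45%, and s = 90% with c = 50% gives 45%.

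**Indicator 2, precision on the restricted base.** Half-width = 1.96 × √(p(1 − p) / (270 × s)).

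| s (assumed) | n = 270 × s | p = 50% | p = 80% |
|---|---|---|---|
| 0.5 | 135 | ±8.4 points | ±6.7 points |
| 0.7 | 189 | ±7.1 points | ±5.7 points |
| 0.9 | 243 | ±6.3 points | ±5.0 points |

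At p = 50%, ±6 points needs 267 patients in the base, so s of about 267/270 = 99%. At p = 80% it needs 1.96² × 0.16 / 0.06² = 170.7, so 171 patients, or s of about 171/270 = 63%.

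**Indicator 1.** Let a be the share with spirometry and b the share of those who also had a bronchodilator test. The written formula gives a and the endpoint wording gives a × b, so the possible excess is a(1 − b). With a assumed at 80%, it is 0, 8 or 20 points at b = 100%, 90% or 75%. If the combined item is scored yes only when both tests were done, and that item supplies the numerator, the excess is zero.

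**The case against.** The strongest defence is that nothing is lost. The study is descriptive, with no hypothesis test (Section 3.5). Section 4 promises a SAP agreed before analysis, and both the allergic-history and the sensitization items are collected and will be tabulated with counts and N missing. On this view the question mark is an unclosed drafting query. This stands as to severity: the gap is recoverable, and a reader should not infer that the primary analysis is beyond repair. It does not remove the point, because Section 4 does not commit the SAP to settling this base, and the one complete formula available to it would mix two quantities.

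A second defence is that the Appendix 1 formula is presented as the guideline's own, so using it is faithful to the stated objective. This stands in part. It is a good reason to report that ratio and to leave the table alone. It does not make the ratio a measure of compliance among the patients to whom the standard applies.

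Three stronger readings are tempting, and the documents do not support them.

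- *That the base could be picked after seeing results.* Section 6.3 does mention real-time statistics on the main outcomes, but then describes the study team's real-time view as recruitment and eCRF completion. Nothing says that indicator results will be viewed before the SAP is agreed.
- *That confirmed allergy biases the indicator by a known amount.* The history item does put confirmed and suspected allergy under one Yes, so membership of the base is unclear. Any figure would need a rule for scoring a blank sensitization item, and none is stated; Section 3.3 provides for marking a variable as unavailable.
- *That indicator 1 will be overstated.* The heading and introducing sentence in Section 4 name both tests, so the formula may be shorthand. With a single combined item, a spirometry-only count might not even be obtainable.

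It may also be said that smaller denominators affect other subgroup indicators too, and that this is not an error in the sample size. Both are true: 267 and 300 reproduce. The precision figures only show what follows from choosing the restricted base.

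**Conclusion.** The point holds and should be fixed before analysis, but it does not invalidate the study. One of eight primary indicators has an undecided denominator, and the all-asthma alternative in Appendix 1 gives c × s, capped at s. Under an assumed c of 80% and s between 0.5 and 0.9, the same care scores 8 to 40 points lower on that base (80 − 72 and 80 − 40). That an open question stands in the text is certain; the size of the gap rests wholly on assumed shares. On the restricted base the planned ±6 points at a 50% proportion is not assured, though it can be met at higher proportions.

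The indicator 1 mismatch is a minor inconsistency of wording, with an effect that may be nil.

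**What to change.** **Indicator 2, in Section 4 and the SAP, before analysis:**

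1. Delete the question mark and name the primary ratio: patients with a history of suspected allergic asthma who had a sensitization study × 100 / all patients with that history.
2. Report the all-asthma ratio of Appendix 1 as a labelled second line, for comparability with the guideline. Leave the Appendix 1 table as it is.
3. State whether patients whose Yes reflects confirmed allergic asthma belong to the base. If they do, complete the sensitization item for them as well.
4. Give n and a 95% interval on the actual base, beside the N missing already planned, and note that ±6 points at a 50% proportion is not assured there.

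**Indicator 1, in Section 4:** change the numerator to patients with both spirometry and a bronchodilator test, matching the combined item in Section 3.3.1.2, and state that yes means both were done.

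**Cost:** wording only, with variables already listed and no extra patients. The statistical price is the wider interval for indicator 2. If confirmed patients are included, their charts must supply the sensitization item, which may mean returning to some charts if data entry has begun.
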